6.3 Clinical Evaluation of OAB / DO

6.3.1 Voiding Diary

Clinical signs and symptoms of OAB / DO will be determined by a daily voiding diary. The participants must complete the diaries for the 7 days prior to the Baseline visit (visit 2), and for 7 days prior to visits 3-8. The participants will also complete the diaries prior to visit 1A to test for compliance and evaluate for some inclusion criteria. The site will contact the participant 7-8 days prior to the scheduled visit (V2-8) to remind the participant to complete the diary. The daily voiding diary will collect standard bladder function and frequency parameters including frequency of micturitions, volume voided and urgency episodes. The urgency questionnaire is a 4 point scale. See Appendix F.

6.3.2 Pad Test

Each participant will record their use of any pads/panty liners (e.g., Poise® pads or Depends®, etc.) in their diary. The participant will bring in pads/diapers worn prior to Visit 1A and for the **three days** prior to Visit 2 (as well as a new pad/diaper to use as a baseline) and for the 3 days prior to all subsequent visits (V3 to V8). Used pads/diapers will be stored in a plastic bag

provided by the site and weighed upon receipt and compared to the clean pad. All pads/diapers used by the participants for the 7 days prior to each visit, will be counted by the participants and entered in the voiding diary by themselves.

6.3.3 King Health Questionnaire and Assessment of Disease State/Treatment

Patients will also complete a disease-specific quality of life tool, the King's Health Questionnaire (KHQ) at Baseline (V2 prior to dosing), V5, V6, V7, and end of study (V8). See **Appendix B**. Patients will also be queried on subjective assessment of their disease state at Baseline (V2), and subsequent visits. Participants will also be asked to evaluate their response to treatment at Visits 3 to 8. Participants will rate their perceived bladder condition severity at Baseline (V2) and Visits 3 to 8 using a 6-validated point rating scale (1, no problems; 2, very minor problems; 3, minor problems; 4, moderate problems; 5, severe problems; and 6, many severe problems). Participants' assessment of their response to treatment will be measured by asking "Has the treatment been of benefit to you?" with possible responses of no benefit; yes, a little benefit; and yes, very much benefit. See **Appendix C**.

6.3.4 International Consultation on Incontinence Questionnaire-Short Form

The International Consultation on Incontinence Questionnaire- Short Form will be completed in this study by all participants at V2, 5, 6, 7, and 8. Please refer to **Appendix E**.

6.2.5 SF-12

The SF-12 which includes 12 questions evaluating general quality of life will be completed in this study by all participants at V2, 5, 6, 7, and 8. Please refer to **Appendix G**.

6.4 Bladder Scan

Residual volume will be measured using a scan of the bladder. This examination will be carried out at the Screening visit (V1) and V4, 6, and 8. At Visit 1 and Visit 8 urine cultures by catheterization should be done after bladder scans are performed. Copies of the bladder scan figures supplied by the device or a report of the examination must be appended to the patients' source documents.

6.5 Physical Evaluation

6.5.1 Physical Examination

A complete physical examination, including a complete urogenital exam, and review of body systems will be performed at V1 to V8 (excluding V1A). Vital signs (pulse, respiratory rate, oral body temperature, and blood pressure) *will be performed at all visits as below (except V1A)*. Height will be obtained at Screening V1 only. Weight will be obtained at Screening V1 and V8. Any untoward clinically significant change from Screening will be recorded on the E-CRF as an adverse event.

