6.5.3 Vital Signs

Vital signs will be performed at all visits as above (excluding V1A). Vital signs should include an apical pulse measurement and brachial blood pressure both taken after 5 minutes resting in the sitting position (standard sphygmomanometry). For all blood pressure measurements, the same arm should be used throughout the study and whether the right or left arm is used should be specified. *Oral body temperature will be obtained at all visits (except V1A).* Any clinically significant changes from screening will be recorded on the E-CRF as an adverse event. Following administration of study drug at V2, BP and pulse will be measured and recorded every 15 minutes for 2 hours.

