9.1 Adverse Events Definitions and Monitoring

9.2 Adverse Event

An adverse event is any unfavorable and unintended diagnosis, symptom, sign (including an abnormal laboratory finding), syndrome or disease which either occurs during the study, having been absent at baseline, or, if present at baseline, appears to worsen.

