
Objectives:
 
Primary: The primary objective of this study is to evaluate occurrence of Adverse Events and their relationship to hMaxi-K following multiple intramuscular (IM) injections into the bladder wall. Two dose levels (16,000 µg and 24,000 µg by IM injection into the bladder wall) in females with moderate OAB/DO of ≥ six months duration are initially planned.
 
 • Treatment Emergent Adverse Events (TEAEs) – frequency and percentage of TEAEs, TEAEs by maximum severity and by relationship to study drug by treatment; summary of any AEs resulting in discontinuation of administration of study drug, serious adverse events (SAEs), and deaths during the study • Secondary: The secondary objectives of this study are to evaluate the following safety parameters: 
 – Clinical laboratory tests - changes and shift (whether the tests are within clinical normal range, whether they are clinically significant) from baseline by treatment – Electrocardiogram – change and shift from baseline (per ECG over-reader) by treatment – Vital Signs (systolic and diastolic blood pressure, and pulse rate) - change and shift from baseline 
The last assessment made prior to dosing of double-blind study drug will be used as the baseline for all analyses of these safety parameters.
 
In addition, efficacy parameters will be evaluated as change from baseline compared to placebo. Comparisons will be made between combined placebo (N = 6) vs. 16,000 µg (N = 6) and 24,000 µg (N = 6) active hMaxi-K group separately, and also between combined placebo and combined active group (N = 12), as well as between treatment comparisons for a dose response analysis. Efficacy evaluations will include the number of micturitions per day, volume per micturition, urgency episodes (1 or greater on urgency scale), and incontinence episodes from voiding diary, and pad weight. Efficacy evaluations will also include the following cystometric evaluations performed by the overreader at week 4 and 24: 1) Detrusor overactivity ≥ 5 cm H₂O (yes/no- INCLUSION CRITERIA); 2) Volume at first desire to void; 3) Detrusor pressure at beginning of voiding (prior to onset of first contraction, either volitional or involuntary); 4) Volume at first involuntary contraction; if detrusor overactivity (DO) present-Not applicable if no DO present; 5) Maximum detrusor pressure at FIRST contraction.
	

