10.1. Adverse Events

Safety summaries will include the incidence of treatment-emergent adverse events (TEAEs), which are defined as any event that began on or after the date of the first treatment dose or worsened in severity or frequency after treatment dose was initiated. Events worsening in severity will be considered new AEs. AEs recorded on the CRF that began prior to treatment and did not worsen in severity will be recorded as medical history will not be included in the AE summary tables and data listings. Any AEs happens in long-term safety follow-up will be reported in a separate listings and not included in the main planned analyses.

All TEAEs will be coded using version 17.1 of Medical Dictionary for Regulatory Activities (MedDRA) and summaries will present data by System Organ Class (SOC) and preferred term (PT).

The following conventions will be followed in summarizing multiple occurrences of an adverse event for a certain assessment period when summarizing data from individual participant:

- Each subject will be counted only once within a body system (SOC) or a preferred term;
- The highest known severity within a body system or a preferred term will be assigned to the event;
- The strongest relationship within a body system or a preferred term will be assigned to the event.

The denominator used for calculation of the percentages will be the number of subjects in the Safety population per treatment.

Specifically, TEAEs will be summarized in the Safety Population. An overall summary of TEAEs, including number of subjects in population, number of subjects with one or more TEAEs, number of participants with one or more Serious TEAEs, number of deaths (if any), and number of subjects experiencing AEs resulting in discontinuation, will be presented in Table 14.3.1.1 by treatment group. The frequency and percentage of AEs by SOC and PT for each treatment group will be presented in Table 14.3.1.2.

The frequency and percentage of AEs related to study drug (Possibly Related, Probably Related, and Definitely Related) by treatment group will be displayed by treatment in Table 14.3.2.

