10.3. Vital Signs

Summary statistics (mean, standard deviation, median, min and max) of vital sign measurements and changes of measurements from predose for vital sign at each time point will be reported for pooled *hMaxi-K* and placebo in Table 14.3.4.3.

Individual vital sign records will be displayed in Listings 16.2.8.1 and 16.2.8.2.

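### Physical-exam and vital-sign adverse events are referenced to Screening in Protocol 6.5 but to baseline elsewhere, so some pre-injection findings can be counted as treatment-emergent

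*Protocol*

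**What the plan says.** **Texts that use Screening or admit Screening-period events**

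- Protocol 6.5.1 (physical examination): "Any untoward clinically significant change from Screening will be recorded on the E-CRF as an adverse event".
- Protocol 6.5.3 (vital signs): "Any clinically significant changes from screening will be recorded on the E-CRF as an adverse event".
- Protocol 9.6 asks for all adverse events on the E-CRF pages, and names those of the Screening period, where applicable, among them.
- Protocol Table 1 schedules adverse event assessment at Visit 1A and, by footnote f, before dosing at Visit 2.

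**Texts that use baseline or the dosing time**

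- Protocol 9.2: an adverse event "either occurs during the study, having been absent at baseline, or, if present at baseline, appears to worsen". Table 1 labels Visit 2 (Day 0) as Baseline and Visit 1 as Day -14.
- Protocol 7.3 and 7.4 put events arising between consent and dosing on the Medical History page. Section 7.4 directs new events or changes reported after dosing to the Adverse Event log, and has the exam and vital signs repeated before dosing to look for changes since screening.
- SAP Synopsis, Objectives, for laboratory tests, ECG and vital signs: "The last assessment made prior to dosing of double-blind study drug will be used as the baseline for all analyses of these safety parameters".
- SAP 10.3 summarises "changes of measurements from predose for vital sign at each time point".
- SAP 10.1 gives this definition of a treatment-emergent event: "any event that began on or after the date of the first treatment dose or worsened in severity or frequency after treatment dose was initiated". Anything that started before treatment and did not become more severe is treated as medical history and left out of the tables and listings.

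**The concern.** The primary objective is the occurrence of adverse events and their relationship to the gene transfer. The rules for what counts as an event, and where it is written down, therefore need to agree. They do not. A clinically significant finding that appears between Visit 1 and the Visit 2 pre-dose assessment, and persists, is an adverse event under 6.5 but is not one under 9.2. A site following 9.6 puts it on the adverse event page; a site following 7.4 puts it in Medical History.

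At stake is whether findings that preceded the injection enter the treatment-emergent tables. Protocol 9.4 bases causality largely on timing relative to administration, so a wrong onset can also affect the judgement of relatedness.

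**Working it through.** There is no figure in the plan to reproduce. The check follows one finding through the rules, and then sizes a single misclassified event.

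**1. How far apart are the two reference points?** Table 1 puts Visit 1 at Day -14 and Visit 2 at Day 0, which is 14 days. Protocol 7.12 limits screening to 14 days (plus or minus 2) unless the sponsor approves more. Protocol 7.2 allows screening results to stand for up to about 4 weeks after Visit 1A when a positive urine culture has been treated. A new finding in this interval is possible.

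**2. What happens to a finding that arises in the interval?**

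| Rule | Adverse event? | Where recorded |
|---|---|---|
| Protocol 6.5.1, 6.5.3 | Yes, changed since Visit 1 | E-CRF, as an adverse event |
| Protocol 9.6 | If it qualifies as an event, yes | E-CRF adverse event page |
| Protocol 9.2 | No, present at baseline, unless it worsens | Not stated |
| Protocol 7.3, 7.4 | Treated as a pre-dose event | Medical History |
| SAP 10.1 | Not treatment-emergent if it began before treatment and did not worsen | Out of tables and listings |

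**3. Does SAP 10.1 catch every such finding?** It catches those with an onset date before the dosing day. Two cases can pass through.

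- *Case (a): first found at the Visit 2 pre-dose exam.* Under 6.5 and 9.6 it is recorded as an event. Section 9.6 asks for the date of onset and does not mention a time. If that date is the dosing day, the event meets the SAP's on-or-after-the-date condition although it preceded the injection. The SAP's Study Day formula (start date minus first-dose date, plus 1) gives Study Day 1, the same as for an event just after injection. The SAP's exclusion of events that began before treatment points the other way, but a date alone cannot show that it applies.
- *Case (b): arose before dosing but not documented at Visit 2.* At Visit 3 or later, an examiner following 6.5 compares with Visit 1, sees a change and may enter a post-dose onset. SAP 10.1 works from the recorded onset and cannot detect this.

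**4. What does one such event do to an incidence?** Inputs are the group sizes in SAP 3.2. The change is 1/N:

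- one dose group, N = 6: 1/6 = 16.7 percentage points
- combined placebo, N = 6: 1/6 = 16.7 percentage points
- combined active, N = 12: 1/12 = 8.3 percentage points

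SAP 10.1 counts each participant once per system organ class or preferred term. The full step therefore occurs only if she has no other event in that category.

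**The case against.** The strongest reply is that the plan already has the safeguards. Visit 2 repeats the exam and vital signs before dosing specifically to find changes since screening. Sections 7.3 and 7.4 send what is found to Medical History. SAP 10.1 excludes pre-treatment events that do not worsen, and the primary endpoint is treatment-emergent events. A site that follows 7.4 to the letter produces neither residual case from a finding seen at Visit 2. Moreover, 6.5 requires a clinically significant change, which is an investigator's judgement, and the same rule applies to both blinded arms.

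Most of this stands. It confines the problem to the two cases above and removes any argument for bias between arms. It does not remove the problem, because 9.6 and Table 1 contradict 7.3 and 7.4 on recording, and because the SAP filter depends on an onset date that cannot separate before from after injection on the dosing day.

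Two further limits are fair. The SAP's pre-dose baseline covers laboratory tests, ECG and vital signs; physical examination is not in that list, so for examinations the conflict is with 9.2 and 7.4. The vital-sign table in SAP 10.3 holds summary statistics, not event counts, and need not match adverse event rates.

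**Conclusion.** The inconsistency is real and lies in operative recording rules for the primary endpoint. Its reach is narrow: cases (a) and (b) only. The size is up to 16.7 percentage points per misclassified event in a group of 6, assuming that participant has no other event in the same category. The documents give no basis for estimating how often either case would occur, so no expected number is offered.

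A reader might infer that adverse event rates in every arm routinely include changes that predate the injection. The documents do not support that: the Medical History rule in 7.3 and 7.4 and the exclusion in SAP 10.1 remove most of them. A reader might also expect that moving the reference from Visit 1 to Visit 2 would reduce chance out-of-range readings. It would not in general, because a single normal Visit 2 reading is as subject to chance variation as a single normal Visit 1 reading. The case for the change is consistency and correct timing relative to injection.

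**What to change.** 1. In Protocol 6.5.1 and 6.5.3, replace Screening with the last pre-dose assessment (Visit 2), in line with 9.2 and the SAP's baseline for vital signs.
2. Reconcile Protocol 9.6, and the pre-dose adverse event assessments in Table 1, with 7.3 and 7.4, so that pre-dose events have one recording location.
3. In SAP 10.1, state that a finding first observed on the dosing day before injection is not treatment-emergent unless it worsens afterwards. Sites must then mark dosing-day entries as before or after injection.

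The first change alone would leave the conflict between 9.6 and 7.3/7.4 in place. None of the three recovers a finding that was simply missed at Visit 2, but later examiners would at least compare with the Visit 2 record.

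The cost is wording, plus a before/after marker for dosing-day entries if the E-CRF lacks one. No procedure is added, since the Visit 2 exam and vital signs are already done before dosing.

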6.5.2 ECG

A 12-lead ECG will be performed at Screening (V1) Baseline (V2 -prior to treatment and 2 hours post treatment), V3, V5 and V8. These ECGs obtained at the study centers, will be forwarded to a central reader for final interpretation by a board-certified cardiologist or physician board certified in ECG interpretation. The over reader will return the results to the study center within 48 hours. This does not negate the responsibility of the staff conducting the study to initially review the ECG and to take appropriate clinical actions. The following parameters will be assessed: heart rate, rhythm, PR interval, RR interval, QT interval, QTcF, QTcB, QRS duration, and overall evaluation. For the Visit 2 pre-dose ECG, if abnormalities or clinically significant changes are noted from V1 screening ECG, then the investigator in conversation with the Sponsor and/or designee will determine the participant's eligibility to proceed with dosing.

6.5.3 Vital Signs

Vital signs will be performed at all visits as above (excluding V1A). Vital signs should include an apical pulse measurement and brachial blood pressure both taken after 5 minutes resting in the sitting position (standard sphygmomanometry). For all blood pressure measurements, the same arm should be used throughout the study and whether the right or left arm is used should be specified. *Oral body temperature will be obtained at all visits (except V1A).* Any clinically significant changes from screening will be recorded on the E-CRF as an adverse event. Following administration of study drug at V2, BP and pulse will be measured and recorded every 15 minutes for 2 hours.

6.6 Laboratory Safety Tests

Laboratory safety tests will be performed at Screening (V1), Baseline (V2) and 1 (V3), 2 (V4), 4 (V5), 12 (V7), and 24 (V8) weeks post dosing with study drug.

The laboratory safety tests include:

- Hematology: V1, V2-V5, V7-V8; Complete blood count (CBC) with differential, platelet count, sedimentation rate (sed. rate), PT and PTT (no PT and PTT at V2 and V4).
- Fasting chemistry: V1, V3-V5, V7-V8; Blood Urea Nitrogen (BUN), creatinine, electrolytes (Na⁺, K⁺, Mg⁺⁺, Ca⁺⁺, CO₂, Cl), albumin, alkaline phosphatase, ALT, AST, GGT, LDH, CPK, total bilirubin, total protein, C-reactive protein (CRP), antinuclear antibody (ANA), and glucose. V4 chemistry testing: Blood Urea Nitrogen (BUN), creatinine, electrolytes (Na⁺, K⁺), C-reactive protein (CRP), glucose, and ANA only.
- At screening, participants of child bearing years must have a serum pregnancy test for beta- HCG if they have not had a hysterectomy. In addition, they must have either a serum FSH >40 IU/L or a history of no menses for more than 12 months to confirm post-menopausal status if a hysterectomy or bilateral tubal ligation has not been done.
- At screening only, participants must have a serum hemoglobin A1c performed

- Urine analysis; Conducted at V1, V1A (by dipstick), V2 (by dipstick), V3-V5, V7-V8; microscopic RBC and WBC, protein, glucose, nitrites, pH, and specific gravity. Dipstick will measure blood, leukocyte esterase and nitrites.
- Urine culture: At Screening Visit 1 and 1A (collect by catheterization) and at V3. At Visit 1A, Visit 5 and Visit 8, prior to cystometry (collect using urodynamic catheter) and repeated with clean void prior to discharge. At Visit 2, collect using urodynamic catheter prior to cystoscopy and first clean voided urine after study drug dosing. If V1A cystometry performed at V1 then urine cultures pre-and post-cystometry should be done using urodynamic catheter before cystometry and repeated with clean void prior to discharge.

6.7 Concomitant Medication

At baseline, a history of concomitant medications taken within the past 2 months with special attention given to treatment with anticholinergics, antispasmodics or antimuscarinic medications (including mirebegron and Botox) will be completed. At subsequent visits, assessments of any changes in medication for all prescription or nonprescription medications will be performed.

6.8 Pharmacokinetics

Urine and blood specimens will be obtained at Visit 2 (pre-dosing and 2-hour post dosing) and Visits 3-8 for analysis of *hSlo* cDNA with PCR. If DSMB states specimens are still positive after 6 months, then the participant will be required to return monthly until 2 consecutive specimens are negative and this may unblind this participant.

Instructions for collection of urine and blood for DNA testing:

Blood

- Collect specimen in heparinized tube
- Centrifuge for 10 minutes at 3000 rpm
- Pipette plasma, freeze immediately and store in labeled plastic vial at -20 (or colder)

Urine

- Collect urine sample in sterile container, label and freeze immediately at -20 (or colder)

6.9 Laboratory Evaluations

A local safety laboratory (for example Quest) will perform analysis of all blood and urine specimens. The blood samples for the safety laboratories evaluations should be taken when the participant is fasting if possible. In addition, the participant should be asked to not perform any strenuous exercise or activities prior to blood sampling.

The urine analysis done immediately prior to cystometry and drug administration will be performed by the PI with a Dipstick™ to see if the Dipstick™ is positive for leucocytes and

nitrites which may be a sign of infection. A spun microscopic evaluation may be required for further evaluation,

Urine and blood specimens that are collected from the participants will have real time PCR testing done for detection of *hSlo* cDNA in the Urology laboratory at the Albert Einstein College of Medicine. It is anticipated that the following amounts of blood will be collected for the following procedures over the 6 month study participation:

Table 8. Blood collection (minimum amount of blood that should be taken)			
Procedure	Visit number	Blood volume drawn (mL)	Total blood volume drawn (mL)
Chemistry	1, 3, 4, 5, 7 and 8	15	90
Hematology	1, 2, 3, 4, 5, 7 and 8	3.0	21
Blood for analysis of hSlo cDNA)	2 (pre- and 2 hr post-dosing), 3, 4, 5, 6, 7 and 8	0.5	4
Minimum volume of blood drawn for study over 6 months:			115 ml

Table 9. Summary of Laboratory Tests By Visit								
	Chemistry Fasting	Hematology	βHCG	HA1c	FSH	Urine Cultures	hSlo Blood/ urine	Urinalysis
Visit 1	◆	◆	◆	◆	◆	1 (one from catheter drainage) – after bladder scan		◆
Visit 1A Cystometry						2 (one from catheter drainage pre-cystoscopy and 1 from first clean void post-cystoscopy)		via dipstick
Visit 2 (Treatment by Cystoscopy)		◆ No PT/PTT				2 (one from catheter drainage pre-treatment and 1 from first void post-treatment)	◆ (blood and urine: pre-dosing and 2 hours post-dosing)	via dipstick (prior to treatment)
Visit 3	◆	◆				1 (clean void)	◆	◆
Visit 4	◆	◆ No PT/PTT					◆	◆
Visit 5 Cystometry	◆	◆				2 (one from catheter drainage pre and 1 from first clean void post)	◆	◆
Visit 6							◆	
Visit 7	◆	◆					◆	◆
Visit 8 Cystometry	◆	◆				2 (one from catheter drainage pre and 1 from first clean void post-treatment); Bladder scan prior to catheterization	◆	◆

